6.5.1.1 Starting dose

The starting dose to be administered to the first cohort of 10 participants will be a single dose of approximately 10⁴ oocysts administered as oral suspension to be taken with approximately one glass of water (approximately 200 mL).

6.5.1.2 Provisional dose levels

Table 6-3 describes the starting dose and the maximum dose level that may be evaluated during this trial; additional doses between $1x10^3$ and $1x10^6$ may be considered.

Table 6-3 Provisional dose levels

Dose level	Oocyst dose (approximate viable oocyst count)
Starting dose	1x10 ⁴
Maximum dose	1x10 ⁶

6.6 Additional treatment guidance

6.6.1 Treatment compliance

Each participant will be supervised while receiving their single dose of ABO809, and will be domiciled for a minimum of 10 days to support compliance with study requirements.

6.6.2 Recommended treatment of adverse events

Based on the expected symptomatology following *Cryptosporidium* administration, treatment to stabilize electrolyte and water homeostasis may need to be initiated. This may include parenteral fluid administration and, in case of persistent clinical symptoms, the administration of medications (see Section 6.2.3).

Any interventions to treat adverse events (AEs) must be recorded on the appropriate eCRF.

6.7 Preparation and dispensation

The study site will be supplied with ABO809 in packaging as described in the Investigational and control drugs section (see Section 6.1.1). A unique medication number will be printed on the study medication label. ABO809 should be prepared/diluted as per the instructions for use provided in the Pharmacy Manual.

6.7.1 Handling of study treatment and additional treatment

6.7.1.1 Handling of study treatment

Study treatment must be received by a designated person at the study site, handled and stored safely and properly and kept in a secured location to which only the investigator and designated site personnel have access. Upon receipt, all study treatment must be stored according to the instructions specified on the labels.

Clinical supplies are to be dispensed only in accordance with the protocol. Technical complaints are to be reported to the respective Novartis Corporate Organization Quality Assurance.

Medication labels will be in the local language and comply with the legal requirements of the country. They will include storage conditions for the study treatment but no information about the participant except for the medication number.

The Investigator must maintain an accurate record of the shipment and dispensing of study treatment in a Drug Accountability Log. Monitoring of drug accountability will be performed by monitors during site visits or remotely and at the completion of the trial. Participants will be asked to return all unused nitazoxanide and packaging at the end of the study or at the time of discontinuation of study treatment.

At the conclusion of the study, and as appropriate during the course of the study, the Investigator will return all unused study treatment, packaging, drug labels, and a copy of the completed Drug Accountability Log to the Novartis monitor or to the Novartis address provided in the Investigator folder at each site.

6.7.2 Instruction for prescribing and taking study treatment

Table 6-4 Dose and treatment schedule

Investigational / Control Drug (Name and Strength)	Dose	Frequency and/or Regimen
ABO809, 3x10 ⁶ CE/3m L	Approximate oocyst count 1x10 ³ - 1x10 ⁶	A single dose on Day 1

Investigational / Control Drug (Name and Strength)	Dose	Frequency and/or Regimen
Nitazoxanide (Rescue medication)	500 mg	Every 12 hours with food for 3 days

7 Informed consent procedures

Eligible participants may only be included in the study after providing (witnessed, where required by law or regulation), IRB/IEC-approved Informed Consent.

Informed Consent must be obtained before conducting any study-specific procedures (e.g. all of the procedures described in the protocol). The process of obtaining Informed Consent must be documented in the participant source documents.

Novartis will review the study site proposed Informed Consent form to ensure it complies with the ICHE6 GCP guidelines and regulatory requirements and is considered appropriate for this study. Any further changes to the proposed consent form suggested by the Investigator must be agreed to by Novartis before submission to the IRB/IEC.

Information about common side effects already known about ABO809 and nitazoxanide can be found in Section 4.5, the Investigator's Brochure (IB) and the USPI for nitazoxanide. This information will be included in the participant Informed Consent and should be discussed with the participant during the study as needed. Any new information regarding the safety profile of ABO809 that is identified between IB updates will be communicated as appropriate, for example, via an Investigator notification (IN) or an aggregate safety finding. New information might require an update to the Informed Consent and must be discussed with the participant.

As per Section 4.6, during a Public Health emergency as declared by Local or Regional authorities i.e. pandemic, epidemic, or natural disaster, that may challenge the ability to obtain a standard written Informed Consent due to limits that prevent an on-site visit, Investigator may conduct the Informed Consent discussion remotely (e.g. telephone, videoconference) if allowable by a local Health Authority.

Guidance issued by local regulatory bodies on this aspect prevail and must be implemented and appropriately documented (e.g. the presence of an impartial witness, sign/dating separate ICFs by trial participant and person obtaining Informed Consent, etc.).

The following Informed Consents are included in this study:

- Main study consent, which also includes:
 - A subsection that requires a separate signature for the 'Optional Consent for Additional Research' to allow future research on data/samples collected during this study
- As applicable, Pregnancy Outcomes Reporting Consent for female participants or the female partners of any male participants who took study treatment Commercially Confidential Information

Confidential

Page **42** of **81** Protocol No. CABO809A02101

Commercially Confidential Information

Women of child-bearing potential must be informed that taking the study treatment may involve unknown risks to the fetus if pregnancy were to occur during the study and agree that in order to participate in the study they must adhere to the contraception requirements.

A copy of the approved version of all consent forms must be provided to Novartis after IRB/IEC approval.

Participants may be asked to complete an optional questionnaire to provide feedback on their clinical trial experience.

8 Visit schedule and assessments

The Assessment Schedule (Table 8-1) lists all of the assessments when they are performed. All data obtained from these assessments must be supported in the participant's source documentation.

Participants should be seen for all visits/assessments as outlined in the Assessment Schedule (Table 8-1) or as close to the designated day/time as possible. Missed or rescheduled visits should not lead to automatic discontinuation.

Participants who discontinue from the study treatment are to return for the end of treatment visit as soon as possible, and attend the follow-up visits as indicated in the Assessment Schedule.

Commercially Confidential Information

The "X" in the table denotes the assessments to be recorded in the clinical database or received electronically from a vendor. The "S" in the table denotes the assessments that are only in the participant's source documentation and do not need to be recorded in the clinical database.

As per Section 4.6, during a Public Health emergency as declared by Local or Regional authorities i.e. pandemic, epidemic, or natural disaster, that limits or prevents on-site study visits, alternative methods of providing continuing care may be implemented by the investigator as the situation dictates. If allowable by a local Health Authority and depending on operational capabilities, phone calls, virtual contacts (e.g. tele consult) or visits by site staff/home nursing staff to the participant home, can replace on-site study visits, for the duration of the disruption until it is safe for the participant to visit the site again.

Participants may be asked to check-in to the study site prior to Day 1 to undergo additional COVID-19 precaution procedures.

Table 8-1 Assessment Schedule

Period	Scree	ning	Treatment			ln-	Patie	nt Fo	llow	-Up						Out	tpatient	t Follow	-Up		
Visit Name	Screening	Baseline	Treatment			lnį	patie	nt Fo	llow-	Up			0	utpat	ient F Visit	ollow	-Up	Safet	y Follo Call	w-Up	End of Study Call
Visit Number	1	2	101	102	103	104	105	106	107	108	109	110	111	112	113	114	115	116	117	118	199
Days	-28 to -2	-1	1	2	102 103 104 105 106 107 108 109 1 2 3 4 5 6 7 8 9 1								14	17	21	24	28	35	42	49	56
Informed consent	Х																				

Understanding of Cryptosporidium Infection & Transmission Quiz	S											
Medical history/current medical conditions	x											
Physical Examination	S	S					S			S		

Period	Scree	ning	Treatment			ln-	Patie	nt Fo	llow-	·Up						Ou	tpatien	t Follow	-Up		
Visit Name	Screening	Baseline	Treatment			lnį	patie	nt Fo	llow-	Up			0	utpat	ient F Visit	ollow	v-Up	Safet	y Follo Call	w-Up	End of Study Call
Visit Number	1	2	101	102	103	104	105	106	107	108	109	110	111	112	113	114	115	116	117	118	199
Days	-28 to -2	-1	1	2	3	4	5	6	7	8	9	10	14	17	21	24	28	35	42	49	56
Inclusion / Exclusion criteria	S	S																			
Demography	Х																				
Alcohol Test, Drug Screen, and Cotinine Test	S	S																			
SARS-CoV2 Screen	Х	Х																			
Hepatitis screen	S																				
HIV screen	S																				
Thyroid stimulating hormone	Х																				
T4 (Free)	Х																				
Pregnancy ²	Х	Х															Х				
Body Height	Х																				
Body Weight ¹¹	Х	X	X ³	Χ	Х	Х	Х	Х	Х	Х	Х	Х	Х	Х	Х	Х	Х				
Vital Signs ¹¹	Х	X	X ³	Χ	Х	Х	Х	Х	Х	Х	Х	Х	Х	Х	Х	Х	Х				
Electrocardiogram (ECG) ¹¹	Х	Х	X 3									х					Х				
Hematology ¹¹	Χ		X ³									Х					Х				
Clinical Chemistry ¹¹	Х		X ³									х					Х				
Urinalysis ¹¹	Х	Х	X ³									Х					Х				
ABO809 administration			х																		

Period	Scree	ning	Treatment			ln-	Patie	nt Fo	llow	-Up						Out	tpatient	t Follow	-Up		-
Visit Name	Screening	Baseline	Treatment			ln	patie	nt Fo	llow-	Up			O	utpat	ient F Visit		/-Up	Safet	y Follo Call	w-Up	End of Study Call
Visit Number	1	2	101	102	103	104	105	106	107	108	109	110	111	112	113	114	115	116	117	118	199
Days	-28 to -2	-1	1	1 2 3 4 5 6 7 8 9 10 14 17 21 24									28	35	42	49	56				
Participants domiciled ¹³							>	<													
Stool Collection 12	Х	Х	Х	Х	Х	Х	Х	Х	Х	Х	X Inforn	Х	X ⁴	X ⁴	X ⁴	X ⁴	X ⁴				
				C	omn	nerc	ially	Con	fide	ntial I	nforn	nation	1								
Occult Blood	Х	X		X		Х		x		X		X									
Cryptosporidium Antigen by EIA ¹⁰ ,	Х	Х	х	Х	Х	Х	х	х	х	х	х	х	Х	х	Х	х	Х				

IgA	Х															
			C	Comr	nerc	тану	Con	muc	muai i	Inforn	natior					

Evaluation of Clinical Signs and Symptoms ⁶	Х	х	Х	Х	х	х	х	х	Х	x	x	x	х	х	х	х	Х		
CHIM Diary		S	S	S	S	S	S	S	S	S	S	S	S	S	S	S	X ¹⁴		
Standard of Care Drug Administration (Nitazoxanide) ⁸															x				

Period	Scree	ning	Treatment			ln-	Patie	nt Fo	llow-	Up						Out	patient	Follow	-Up		
Visit Name	Screening	Baseline	Treatment			In	patie	nt Fo	llow-	Up			O	utpat	ient F Visit	ollow s	-Up	Safet	y Follo Call	w-Up	End of Study Call
Visit Number	1	2	101	102	103	104	105	106	107	108	109	110	111	112	113	114	115	116	117	118	199
Days	-28 to -2	-1	1	2	3	4	5	6	7	8	9	10	14	17	21	24	28	35	42	49	56
Concomitant medications	Х	х	Х	Х	Х	х	х	Х	Х	Х	х	Х	х	Х	Х	Х	Х	Х	Х	Х	Х
Adverse Events	Х	Х	Х	Х	Х	Х	Х	Х	Х	X	Х	Х	Х	Х	Х	Х	Х	Х	Х	Х	X

Safety Follow-Up Call for Study Participants								S	S	S	S
Study completion information											Х

Period	Post-Stud	dy Follow-Up
Visit Name	Post-Study	Follow-Up Call
Days	6 Month Phone Contact	12 Month Phone Contact
Informed consent		

Understanding of Cryptosporidium Infection	
& Transmission Quiz	

Period	Post-Study Follow-Up		
Visit Name	Post-Study Follow-Up Call		
Days	6 Month Phone Contact	12 Month Phone Contact	
Medical history/current medical conditions			
Physical Examination			
Inclusion / Exclusion criteria			
Demography			
Alcohol Test, Drug Screen, and Cotinine Test			
SARS-CoV2 Screen			
Hepatitis screen			
HIV screen			
Thyroid stimulating hormone			
T4 (Free)			
Pregnancy ²			
Body Height			
Body Weight ¹¹			
Vital Signs ¹¹			
Electrocardiogram (ECG) ¹¹			
Hematology ¹¹			
Clinical Chemistry ¹¹			
Urinalysis ¹¹			
ABO809 administration			
Participants domiciled ¹³			
Stool Collection ¹²			
	Commercially Confidential Informat	tion	
Occult Blood			
Cryptosporidium Antigen by EIA ^{10, 12}			

Period	Post-Study Follow-Up		
Visit Name	Post-Study Follow-Up Call		
Days	6 Month Phone Contact Commercially Confidential Information	12 Month Phone Contact on	
lgA			
	Commercially Confidential Informa	tion	
Evaluation of Clinical Signs and Symptoms ⁶			
CHIM Diary			
Standard of Care Drug Administration (Nitazoxanide) ⁸			
Concomitant medications			
Adverse Events	S ¹⁵	S ¹⁵	
•	Commercially Confidential Information	on	
Safety Follow-Up Call for Study Participants	S	s	
Study completion information			

Commercially Confidential Information

² Serum pregnancy tests at Screening and Day 28. Urine pregnancy test at Baseline.

³ Before ABO809 administration.

⁴ Participants should make every attempt to bring self-collected stool specimen to the clinic for each Outpatient Follow-Up visit. In the 24 hours prior to each Outpatient Follow-Up visit, all stools should be collected.

⁵ During screening, the first diarrheal stool, and the first diarrheal stool with relapse after clinical clearance will be tested for enteral pathogenic micro-organisms.

⁶ Includes number and frequency of diarrheal episodes, stool weight, volume, and grading (see Section 8.3.2, Section 8.4.1, and Appendix 1). Additionally, includes evaluation of nausea, vomiting, abdominal pain or discomfort, abdominal tenderness, abdominal rebound, abdominal distension, fecal urgency, diarrhea, flatulence, tenesmus, poor appetite, dehydration, fever, and electrolyte imbalance

⁸ Nitazoxanide to be administered per Prescribing Information (i.e. 500 mg every 12 hours for 3 days). Nitazoxanide administration will be captured on the standard concomitant medication page, and no specific CRF is required.

Page **50** of **81** Protocol No. CABO809A02101

Period	Post-Study Follow-Up	
Visit Name	Post-Study Follow-Up Call	
Days	6 Month Phone Contact	12 Month Phone Contact

¹¹ Additional tests can be done at the discretion of the Investigator e.g., in the case of dehydration.

Commercially Confidential Information

¹³ All participants, whether or not they are symptomatic, will be domiciled in a unit until completion of Day 10 assessments. Participants who experience symptoms will remain domiciled for the duration of the diarrheal illness up to a maximum of Day 21. If a participant experiences diarrhea after Day 10 (after the participant has been discharged from the study site), the participant may be readmitted, at the discretion of the Investigator, to remain domiciled until the cessation of symptoms or Day 21. whichever is earlier.

¹⁴ CHIM diary eCRF page will capture only if the diary was fully complete or not. No data from the diary will be recorded on this diary eCRF page. AEs will be captured on the standard AE eCRF, and nitazoxanide administration will be captured on the standard concomitant medication eCRF page.

¹⁵ Adverse events of special interest (AESI) defined in Section 10.1.1.1 will be recorded at the 6 and 12 month Post-Study Follow-up calls as source data and reported to Novartis Safety if the Investigator considers there is a reasonable possibility that ABO809 caused the event, unless otherwise specified by local law/regulations.

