The study will consist of three (to a maximum of six) sequential cohorts of approximately 10 participants each. The cohorts will be dosed one after the other for a total of 30 (to a maximum of approximately 60) participants. This is an adaptive study and for a particular cohort, safety, incidence of infection and incidence of clinical illness will be evaluated on Day 14 to inform whether the ABO809 dose needs to be changed for dosing of the next cohort (see Section 6.5.1). If there are no safety issues, and the expected incidence of infection and illness are observed in one cohort, the next cohort will be dosed at the same dose level (see Section 6.5.1 for details). If the dose of ABO809 is changed from one cohort to the next, additional cohorts may be added to further evaluate Cryptosporidium infection and clinical illness following dosing with ABO809.

The study will consist of up to a 28-day Screening/Baseline period, an ABO809 administration and inpatient monitoring period, an outpatient follow-up period, and a study completion evaluation on Day 56. Additionally, Post-Study Follow-Up Calls will be conducted at 6 and 12 months after ABO809 administration. A CHIM diary will be provided to each participant to collect information on the participant's clinical symptoms.

Participants will receive a single oral dose of ABO809 on Day 1.

Cryptosporidium infection is defined as the presence of oocysts in at least 1 stool sample starting 72 hours following the administration of ABO809 (or sooner if associated with symptoms suggestive of diarrheal illness) and up to Day 10.

If clinical symptoms associated with cryptosporidiosis occur earlier than 72 hours post-administration, then stool samples after the onset of symptoms can be collected for parasitological evaluation for the primary endpoint. Normal bowel transit time varies from 30 to 40 hours, and therefore \geq 72 hours is chosen to minimize the chance of detecting only passively excreted oocysts given orally.

Resolution of *Cryptosporidium* infection is defined as no evidence of *Cryptosporidium* in stool samples collected over ≥ 2 consecutive days.

Stool samples will also be collected and sent to the laboratory in instances of relapse symptoms suggestive of *Cryptosporidium* infection until Day 28. Participants experiencing diarrheal symptoms between Day 28 and Day 56 may return for an unscheduled visit and provide stool for assessment of *Cryptosporidium* infection.

[figure not shown]

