3.2 ABO809 administration and inpatient monitoring period

ABO809 will be administered at the study site on Day 1. All participants, whether or not they are symptomatic, will be domiciled in a unit with adequate infection control until completion of Day 10 assessments. Participants who experience symptoms will remain domiciled for the duration of the diarrheal illness up to a maximum of Day 21. After Day 10, participants will be released from the study site only after they have had no diarrheal stools for at least 24 hours. Signs, symptoms, stool characteristics and parasitological assessment of oocyst shedding will be monitored daily. Safety assessments will include physical exams, ECGs, vital signs, standard clinical laboratory evaluations (hematology, blood chemistry, and urinalysis), adverse event and serious adverse event monitoring (see Table 8-1).

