3.3 Follow-up period and End of Study

Participants will return for outpatient follow-up visits on Day 14, 17, 21, 24, and 28 for clinical assessments and to provide collected stool samples for analysis. To minimize the risk of long term asymptomatic shedding and recurrence, participants may receive nitazoxanide per the U.S. Prescribing Information (see Section 6.2.3).

If a participant experiences diarrhea after Day 10 (after the participant has been discharged from the study site), the participant may be readmitted, at the discretion of the Investigator, to remain domiciled until the cessation of symptoms or Day 21, whichever is earlier. If diarrhea is not associated with any additional risks to participants, the Investigator can decide that the participant can be managed in an outpatient setting. In this case, the participant is requested to make a reasonable effort to collect all diarrheal stool samples for delivery to the study site. If a participant is still experiencing diarrheal illness at Day 28, the participant's stool will be analyzed for ongoing shedding of oocysts and the participant may be referred to specialty care for further diagnostic work-up and treatment at the discretion of the Investigator.

All participants will return for a follow-up visit on Day 28 to provide collected stool samples. A physical examination and laboratory tests will also be conducted.

Commercially Confidential Information

Alternatively, between

Day 28 and Day 56, participants may seek medical support from his/her healthcare provider (HCP). Participants may come back to the study site for an unscheduled visit until EOS. The end of study (EOS) visit will occur on Day 56 via phone call. Additional Post-Study Follow-Up phone calls will be conducted after EOS at 6 and 12 months after ABO809 administration. During the phone calls, data will be collected on the development of new onset persistent symptoms that may be related to administration with ABO809, including but not limited to diarrhea, abdominal pain, eye pain and joint pain in all participants (see Section 10.1.1.1).

4 Rationale

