Outpatient follow-up period: After the domicile period, participants will be followed on an outpatient basis ending on Day 56 following the ABO809 administration. Infection is expected to be self-limiting in healthy adults and resolve by Day 21. Published literature on the intensity of infection and oocyst excretion patterns of *C. parvum* in healthy volunteers suggests that oocyst excretion is limited to the first 14 days in up to 86% participants with diarrhea, and excretion prolonged beyond 28 days is observed in only 5% of participants (Chappell et al 1996). Participants will return for follow-up visits on Day 14, 17, 21, 24 and 28 for physical examination and/or to provide collected stool samples (for measurement of oocyst shedding) (see Table 8-1). Safety Follow-Up Calls will be conducted with participants up to Day 56 to collect adverse events that are considered related to administration with ABO809 (see Section 10.1.1.1). Any participants who experience diarrheal symptoms between Day 28 and Day 56 may provide a stool sample for analysis and may return to the study site for an unscheduled visit to consult with the Investigator.

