8.3 Efficacy

8.3.1 Cryptosporidium Antigen by EIA

To assess the incidence of *Cryptosporidium* infection, fresh stool samples will be collected at Screening and during the study as detailed in the Assessment Schedule (see Table 8-1). While participants are domiciled, all stools will be collected for grading and quantity record, however, up to 3 stool samples per day, each separated by approximately 4 hour intervals, will be analyzed by EIA CCI at a CLIA laboratory for parasitological assessment of oocyst shedding. If the participant passes less than 3 stools on any given day during domiciling (1 or 2) then these stool samples will be used for parasitological assessment.

Commercially Confidential Information

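### For participants discharged around Day 10 while still shedding, scheduled stool collection does not give the two consecutive negative days that define resolution, and the SAP's last-positive rule then dates resolution early, by up to about 3 days

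*Protocol*

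**What the plan says.** Protocol section 3 and SAP 2.1.1.1 both define resolution of infection as no evidence of Cryptosporidium "in stool samples collected over ≥ 2 consecutive days". Time to resolution of infection is a secondary endpoint. SAP 2.5.2 presents it with Kaplan-Meier curves and a median with a 90% confidence interval.

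Sampling has two phases:

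- **Domiciled.** Under Protocol 8.3.1, "up to 3 stool samples per day, each separated by approximately 4 hour intervals, will be analyzed by EIA". Everyone stays until the Day 10 assessments. Under Protocol 3.2, "Participants who experience symptoms will remain domiciled for the duration of the diarrheal illness up to a maximum of Day 21". Release after Day 10 depends on diarrhea, not shedding: "participants will be released from the study site only after they have had no diarrheal stools for at least 24 hours".
- **Outpatient.** Protocol 3.3: "Participants will return for outpatient follow-up visits on Day 14, 17, 21, 24, and 28 for clinical assessments". Footnote 4 to Table 8-1: "In the 24 hours prior to each Outpatient Follow-Up visit, all stools should be collected". If diarrhea after Day 10 is managed at home, "the participant is requested to make a reasonable effort to collect all diarrheal stool samples for delivery to the study site". Protocol section 3 adds stools for relapse symptoms until Day 28.

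SAP 2.1.1.1 sets the number of days to resolution at 48 hours after the last positive EIA, calculated as the last positive date minus the dosing date plus 3. For outpatients without diarrheal symptoms it counts positives only up to Day 20 and before nitazoxanide. SAP 2.5.3 censors the Kaplan-Meier curves at rescue medication.

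**The concern.** Three texts describe one endpoint and do not fit together. The definition needs negatives on at least two consecutive days. The outpatient schedule supplies isolated 24-hour windows three to four days apart. The SAP formula needs no negatives at all: it adds a fixed two days to whichever positive was seen last.

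The gap falls where clearance is expected. Protocol 1.1 expects natural resolution in approximately 7-21 days, and Protocol 4.1 expects it by Day 21. Protocol 4.1 also reports that "oocyst excretion is limited to the first 14 days in up to 86% participants with diarrhea". If many participants stop shedding after discharge, their dates will be set by the visit calendar, and the Kaplan-Meier median will be pulled early. Recrudescence and reinfection are both defined as occurring after resolution, so they inherit the same date. Natural clearance time also matters for a model meant to evaluate future therapies.

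**Working it through.** The plan gives no figure for this point, so there is none to reproduce. The check is a count over the sampling calendar.

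**Inputs.** Sampled days for a Day 10 discharge: Days 1-10 daily (Protocol 8.3.1), then 14, 17, 21, 24 and 28 (Protocol 3.3 and Table 8-1 footnote 4). SAP rule: last positive date − dosing date + 3. Dosing is on Day 1, so a last positive on Day L gives (L − 1) + 3 = L + 2.

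**Assumptions, not in the documents.** Shedding every day up to a true last day T, a perfectly sensitive assay, and discharge on Day 10.

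**Step 1: coverage.** Gaps between sampled days from Day 10 are 4, 3, 4, 3 and 4 days. From Day 10 to Day 21, collection covers 3 × 24 = 72 of 11 × 24 = 264 hours (27%). The longest unbroken outpatient window is 24 hours.

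**Step 2: can two consecutive negative days be observed?** For T = 8, Days 9 and 10 are both sampled, so yes. For T = 9 only Day 10 remains before discharge. For every T from 9 to 21 no scheduled pair exists when each window is read as one day.

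**Step 3: what date does the SAP give?** The benchmark is T + 2, the same rule under daily sampling.

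| True last shedding day T | Last positive seen, L | SAP date, L + 2 | Daily-sampling date, T + 2 | Error (days) |
|---|---|---|---|---|
| 10, 11, 12, 13 | 10 | 12 | 12, 13, 14, 15 | 0, −1, −2, −3 |
| 14, 15, 16 | 14 | 16 | 16, 17, 18 | 0, −1, −2 |
| 17, 18, 19, 20 | 17 | 19 | 19, 20, 21, 22 | 0, −1, −2, −3 |

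Eleven possible last days collapse onto three dates: 12, 16 and 19. With T uniform over Days 10-20 the mean error is −(6 + 3 + 6)/11 = −15/11 = −1.36 days, and the largest is −3.

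**Step 4: the more generous reading.** Suppose each 24-hour window also yields a stool on the previous calendar date (Days 13, 16 and 20). The errors for T = 10 to 20 become 0, −1, −2, 0, 0, −1, 0, 0, −1, −2, 0. The mean is −7/11 = −0.64 days and the largest is −2. A negative pair on two dates then becomes possible from Day 14, provided stools are passed on both dates.

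**Step 5: dilution.** If a share f of infected participants has last shedding in this range after a Day 10 discharge, the mean shift over all infected participants is f × 1.36 days under the Step 3 reading. The documents do not give f. For assumed values of 0.25, 0.5 and 1, the shift is 0.3, 0.7 and 1.4 days.

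**The case against.** The strongest reply is that the SAP already supplies an operational rule. Its 48 hours is an offset added to the last positive, not a required run of observed negatives, so every infected participant who turns negative before rescue receives a date. This stands. A reader might infer that resolution cannot be shown, or that most participants will be reported as unresolved. The planned analysis does neither. The fault is an unconfirmed, early date, not a missing one.

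Other parts also stand:

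- The definition says consecutive days, not 48 continuous hours, and a 24-hour window can touch two dates. Step 4 allows for this: the error shrinks but does not vanish.
- Visit windows are not the only outpatient stools. Diarrheal and relapse stools are collected, and extended domicile brings daily sampling. These help symptomatic participants only. Protocol 4.1 expects that 30% or more may stay asymptomatic, and the public text gives asymptomatic shedders nothing extra.
- Footnotes 10 and 12 to Table 8-1, on EIA and stool collection, are not in the public text and may add collection.
- It is tempting to say that most participants clear inside the gap. The 86% is an upper figure for participants with diarrhea, and no share clearing by Day 8 or Day 10 is given.
- Censoring at rescue leaves the Day 24 and Day 28 windows little role in time to resolution, so they are not counted here.
- A reader might extend the point to the persistent-shedding event of special interest. That event needs a positive after nitazoxanide, not two negative days. Day 28 is the only clearly post-treatment visit just for those who start on Day 21.

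**Conclusion.** The point holds in limited form. For participants discharged around Day 10 and still shedding on about Day 9 or later, scheduled collection does not provide the two consecutive negative days in the definition. When last shedding falls between visits, the SAP date is early: by 1.36 days on average and 3 at most if each window is read as the visit day, or 0.64 and 2 if it also captures the day before. Both means assume last shedding uniform over Days 10-20, daily shedding and perfect sensitivity.

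The direction is firmer than the size. Without false positives, the last positive seen cannot fall after the last true shedding day, so the date is never late. How far the median moves depends on the share affected, which the documents do not give. Participants who clear by Day 8, or who remain domiciled, are not affected. The primary endpoint, which ends at Day 10, is untouched.

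**What to change.** **Analysis (wording and programming, no new samples).** In SAP 2.1.1.1 and 2.5.2:

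- Treat outpatient-phase resolution of infection as interval-censored between the last positive and the first subsequent negative sample, each plus the two-day offset. Last positive Day 10 with negative Day 14 gives Day 12 to 16; Days 14 and 17 give 16 to 19; Days 17 and 21 give 19 to 23. These contain every daily-sampling date in the table above.
- Right-censor at rescue medication, and do not use samples taken after rescue starts as the negative end of an interval. State whether rescue censoring applies to the sample date or the offset date, because the offset can carry an interval past Day 21.
- Use an interval-censored (Turnbull) estimate in place of the Kaplan-Meier analysis of the last-positive-plus-3 date. Daily-sampled participants enter with one-day intervals.
- State that a single isolated negative visit is not confirmed resolution.
- Reconcile the definition in Protocol section 3, footnote 4 to Table 8-1 and the SAP derivation.

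The cost is wider intervals for the resolution date and a less precise median, which reflects what the samples can show.

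**Collection (optional).** Extend self-collection to the 48 hours before the Day 14, 17 and 21 visits, with at least one EIA per 24 hours. This costs about 3 extra stools and EIAs per participant. Under the Step 4 assumptions it gives a consecutive negative pair for last shedding on Days 9-19 and limits the error to 2 days. Pairs ending on Day 21 fall at the nitazoxanide time point, so they count only if rescue has not started.
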